### 2. Objectives (include all primary and secondary objectives)

#### **Specific Aim 1: Identify patients who would benefit from early use of the OWSV.**

Hypothesis 1a: Several factors such as age, sex, educational level, primary diagnosis, indication for tracheostomy, co-morbidities, and severity of illness will significantly contribute to early tolerance of the OWSV.

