**Sequence and timing:**

- A. Screening by Tracheostomy Nurse Practitioner following percutaneous tracheotomy
1. Glasgow Coma Scale (GCS)
  2. Richmond Agitation Sedation Scale (RASS)
- B. Speech-Language Pathologist consult is placed for patients meeting study inclusion criteria
- C. Patient consent is obtained by Tracheostomy Nurse Practitioner or Speech-Language Pathologist
- D. Randomization into Intervention and Control groups
- E. Session 1 within 12-24 hours following percutaneous tracheotomy:
1. Both groups complete pre-assessment consisting of the following:
    - i. Electronic Patient Records (POE, EPR, or EPIC)
      1. Demographic Data
      2. Patient Characteristics
      3. Sequential Organ Failure Assessment (SOFA)
    - ii. Confusion Assessment Method for the ICU (CAM-ICU)
    - iii. Health-related quality of life survey, Quality of Life – Mechanical Ventilation (QOL-MV)
    - iv. Tracheostomy-related assessment
      1. Trach size
      2. Mechanical ventilation status
      3. Secretions & tolerance of cuff deflation
      4. Presence of complications
        - i. Bleeding at stoma
        - ii. Subcutaneous air
        - iii. Infection at stomal site
        - iv. Pneumothorax
        - v. Accidental decannulation
  2. Intervention Group completes standard SLP evaluation and OWSV trial:
    - i. SLP evaluation includes the following to assess candidacy for OWSV trial:
      1. Level of alertness
      2. Cranial nerve exam
      3. Ability to cough
      4. Ability to tolerate cuff deflation
      5. Ability to tolerate finger occlusion
      6. Vocal quality
    - ii. If appropriate, OWSV will be trialed and assessed for the following:
      1. Duration of tolerance
      2. Change in vital signs
      3. Vocal quality
      4. Presence of air trapping
      5. Sentence Intelligibility Test
    - iii. Recommendations are made for OWSV use outside of SLP supervision
      1. Supervision requirement (RN, Respiratory therapist, trained family, independent)
      2. Duration of OWSV use
  3. Control Group receives no further evaluation or treatment during Session 1, which constitutes current standard of care.
- F. Session 2 within 48-60 hours following percutaneous tracheotomy:
1. Both groups complete post-assessment:

Date: 2/06/18

Principal Investigator: [name]

Application Number: IRB00080981

[figure not shown]
- i. Electronic Patient Records (POE, EPR, or EPIC)
    1. Demographic Data
    2. Patient Characteristics

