**Instruments:**

Name	Concept measured	Number of items
QOL-MV	Quality of life in mechanically ventilated patients questionnaire	12
SIT	Sentence intelligibility test	11
SOFA	Sequential Organ Failure Assessment Tool	6
Additional questions	Demographic Data	

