## 7. Study Statistics

- a. Primary outcome variable.

Speech intelligibility

- b. Secondary outcome variables.

- Patient characteristics
- Quality of Life
- Complications
- Time to events
- Length of stay
- Mortality

\*See codebook for list of additional variables

- c. Statistical plan including sample size justification and interim data analysis.

Mean, standard deviation, median and inter-quartile range will be calculated for continuous variables. Paired t-tests will be used to compare pre and post assessment scores for continuous variables. Frequencies and percentages will be calculated for categorical variables. Chi square and Fisher Exact tests will be used to compare pre and post assessment scores of categorical variables. Sample size is estimated based on 30% of tracheostomy patients who might be awake and interactive at the Johns Hopkins Hospital in 2016, as per the tracheostomy database. According to the 2014 data, we found that about 55 patients were awake and interactive while having a percutaneous tracheostomy tube at the hospital. Considering a 10% of the patients who may not be interested in the study, we will plan for a sample size of 50 with 25 in the intervention group and 25 in the control group.

- d. Early stopping rules.

If patients have changes in clinical condition that prevents cuff deflation, they will be dropped from the study. The study will be halted if any major complications occur from early trial of OWSV.

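### For the between-arm Hypotheses 2a and 3a, section 7c names only within-patient tests and leaves Session 1 QOL-MV, SOFA and ventilation status out of the arm comparison, at a cost in precision

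*Combined protocol and SAP*

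**What the plan says.** **Analysis.** Section 7c gives one test for continuous outcomes: "Paired t-tests will be used to compare pre and post assessment scores for continuous variables". For categorical outcomes it says "Chi square and Fisher Exact tests will be used to compare pre and post assessment scores of categorical variables". Apart from descriptive statistics, nothing else is named: no regression, no covariate and no between-arm test.

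**Questions.** Hypotheses 2a (speech intelligibility, the primary outcome in section 7a) and 3a (quality of life) both predict a larger pre-to-post increase in the early arm than in the standard arm.

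**Data available.** Under Sequence and timing, the Session 1 pre-assessment in both groups covers the QOL-MV, SOFA and, within the tracheostomy-related assessment, "Mechanical ventilation status". All of this precedes the intervention group's valve trial. The Sentence Intelligibility Test (SIT) is listed at Session 1 only as part of that valve trial, so only in the intervention group and only in patients judged suitable.

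**Population and instrument.** The Instruments table describes the QOL-MV as "Quality of life in mechanically ventilated patients questionnaire". Ventilation is not an inclusion criterion in section 5, and the abstract speaks of valve use on or off the ventilator.

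**Size.** Section 7c says "we will plan for a sample size of 50 with 25 in the intervention group and 25 in the control group". The randomisation step names no stratification factor.

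**The concern.** A paired t-test within each arm, or over all patients, shows whether scores moved. It does not show whether they moved more in one arm. Hypotheses 2a and 3a need an arm comparison, and whoever writes it must decide what to adjust for. If it defaults to a plain two-sample test, baseline information already collected in both arms goes unused.

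That matters more than usual here. There are only 25 patients per arm, nothing is stratified, and patients on and off the ventilator may be enrolled together. The quality-of-life questionnaire is written for ventilated patients, so ventilation status plausibly bears on its score. SOFA is the recorded measure of severity, which Hypothesis 1a already treats as important in another context: "co-morbidities, and severity of illness will significantly contribute to early tolerance of the OWSV". At stake is the precision of a small trial, and how far its one realised estimate can be trusted if the arms differ on these variables by chance.

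**Working it through.** **1. The plan's own figure.** Section 7c starts from 2014 data ("we found that about 55 patients were awake and interactive while having a percutaneous tracheostomy tube at the hospital") and allows for refusal ("Considering a 10% of the patients who may not be interested in the study"). 55 × (1 − 0.10) = 49.5, rounded to 50. The figure reproduces. It is a feasibility count: no alpha, power, effect size or SD is given, so there is no power figure to check.

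**2. Chance imbalance in ventilation status.** Assume a ventilated share p, which the documents do not give, and let each arm's count be Binomial(25, p). A gap of 20 percentage points is 0.20 × 25 = 5 patients.

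| p (assumed) | P(gap of 5 or more) |
|---|---|
| 0.5 | 20.3% |
| 0.6 | 19.3% |
| 0.7 | 16.4% |

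If the total ventilated is instead held fixed, the answer depends on whether that total is odd or even: 22-26% for totals of 15, 25 or 35, and about 15% for 20, 24 or 30. The binomial figures average over this.

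In SD units, 20 points at p = 0.5 is 0.20 / √(0.5 × 0.5) = 0.40 SD.

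**3. What an imbalance does to an unadjusted two-sample test.** The material here is a simulation of 40,000 trials per setting, with 25 per arm, one standardised covariate, no true effect and a two-sided 5% level. R² is the assumed share of outcome variance that the covariate explains.

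| R² (assumed) | Type I error, all trials | Unadjusted, imbalance above 0.4 SD (about 16% of trials) | Adjusted, same trials |
|---|---|---|---|
| 0.1 | 0.050 | 0.08 | 0.05 |
| 0.3 | 0.050 | 0.14 | 0.05 |
| 0.5 | 0.049 | 0.18 | 0.05 |

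Over all randomisations the unadjusted test holds its level. The error appears only conditionally, in trials with a sizeable imbalance.

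**4. Precision from adjusting for two covariates.** With N = 50 and k = 2 covariates, the ratio of unadjusted to adjusted variance is approximately [(N − k − 3)/(N − 3)] / (1 − R²) = (45/47) / (1 − R²).

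| R² (assumed) | Formula | Simulation |
|---|---|---|
| 0 | 0.96 | 0.96 |
| 0.03 | 0.99 | 0.98 |
| 0.05 | 1.01 | 1.00 |
| 0.1 | 1.06 | 1.06 |
| 0.2 | 1.20 | 1.19 |
| 0.3 | 1.37 | 1.36 |

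Break-even is at R² = 2/47 = 4.3%, so about 5%. For QOL-MV the relevant R² is what ventilation status and SOFA explain beyond the Session 1 QOL-MV score.

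**5. In terms of detectable effect.** With two-sided alpha 0.05 and 80% power (both assumed), the unadjusted detectable difference is (1.960 + 0.842) × √(2/25) = 0.79 SD. At R² = 0.3 it is 0.79 × √0.7 = 0.66 SD, before the small degrees-of-freedom cost in step 4.

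**The case against.** The strongest reply is that nothing here is invalid. The sentence in section 7c describes a within-patient test, so between-arm imbalance does not enter it directly. Once an arm comparison is written, randomisation makes an unadjusted one valid, and chance imbalance is already part of its standard error. Section 4a labels the trial a pilot, where covariate adjustment is good practice rather than a requirement. The gain rests on R² values that no section supplies, and the Session 1 QOL-MV score may already absorb much of what ventilation status explains.

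Most of that stands, and it limits the point. A reader might infer that the results will be biased or that false positives are inflated; step 3 shows otherwise over all randomisations. A reader might also infer that the protocol itself says ventilation or SOFA drives quality of life. It does not: Hypothesis 1a names severity, not ventilation, and only for valve tolerance. Tolerance is a predictor question under Aim 1, where no arm comparison is at issue.

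Nor can a baseline SIT score be added to the model for the primary outcome, since the control arm has none listed.

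What the reply does not remove is that an arm comparison must still be specified, that its covariates are best fixed in advance, and that suitable ones are already collected in both arms.

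One caution: as listed, the pre-assessment follows randomisation, and section 4c says patients are not blinded. Session 1 values precede the valve trial but not necessarily knowledge of the allocation. This matters more for the self-reported QOL-MV than for SOFA or ventilation status.

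**Conclusion.** The point holds as a matter of missing specification and lost efficiency. For Hypotheses 2a and 3a the plan names a test that does not compare the arms, and it leaves usable Session 1 information out of that comparison.

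The size is modest and conditional. A ventilation gap of 20 points or more has probability 16-20%, assuming 50-70% ventilated. Adjustment for ventilation status and SOFA is worth about 6% more patients if they explain 10% of the remaining variance, and about 19-36% at 20-30%. It is worth nothing, or costs up to about 4%, below about 5%. All the R² values are assumptions, as is the link from ventilation status to QOL-MV. The case for acting is that the possible loss is negligible and the possible gain is not, in a trial whose size was set by availability.

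**What to change.** Amend section 7c before any outcome data are examined.

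- **Hypothesis 3a:** replace the paired t-test with a prespecified linear model of Session 2 QOL-MV on arm, Session 1 QOL-MV, Session 1 ventilation status (on/off) and Session 1 SOFA. Report the arm coefficient with its 95% confidence interval.
- **Hypothesis 2a:** compare Session 2 SIT scores between arms in a linear model with arm, Session 1 ventilation status and Session 1 SOFA. Include no Session 1 SIT term. Hypothesis 2a is worded as an increase from pre to post, so it should be reconciled with what is measured in controls. The plan should also state that SIT is scored at the Session 2 valve trial in both arms; at present it is itemised only under Session 1.
- **Covariates:** use Session 1 values only, not ventilation status or SOFA from Session 2, which follow the intervention. Add no others after seeing the data.
- **Paired tests:** keep them, if wanted, as descriptions of change within each arm.

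The cost is a paragraph of SAP text, two or three degrees of freedom out of about 48, and at worst a precision loss of about 4%. No new data, visits or patients are needed.

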    3. Sequential Organ Failure Assessment (SOFA)
  - ii. Health-related quality of life survey (QOL-MV)
  - iii. Confusion Assessment Method for the ICU (CAM-ICU)
  - iv. Tracheostomy-related assessment
    1. Trach size
    2. Mechanical ventilation status
    3. Secretions & tolerance of cuff deflation
    4. Presence of complications
      - i. Bleeding at stoma
      - ii. Subcutaneous air
      - iii. Infection at stomal site
      - iv. Pneumothorax
      - v. Accidental decannulation
  2. Intervention Group completes second SLP evaluation and OWSV trial.
  3. Control Group completes initial SLP evaluation and OWSV trial.
- G. Session 3 following first trach change
1. Both groups receive follow-up SLP re-evaluation and OWSV trials as appropriate per standard of care.

**Setting:** All ICUs at the Johns Hopkins Hospital

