## 5. Inclusion/Exclusion Criteria

### Inclusion Criteria:

- Patient who received a percutaneous tracheostomy
- Glasgow Coma Scale score  $\geq 9$
- Confusion Assessment Method –ICU (CAM-ICU): negative
- Richmond Agitation Sedation Scale (RASS): -1 to +1
- Able to understand English

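### Section 7c compares categorical scores before and after in the same patients with chi-square and Fisher exact tests, which do not handle paired data

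*Combined protocol and SAP*

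**What the plan says.** Section 7c (Study Statistics) gives one rule for categorical data: "Chi square and Fisher Exact tests will be used to compare pre and post assessment scores of categorical variables". Just before it, the rule for continuous data is: "Paired t-tests will be used to compare pre and post assessment scores for continuous variables".

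The schedule in section 4a (Sequence and timing) shows that the two measurements come from the same people. At Session 1, "Both groups complete pre-assessment consisting of the following", and at Session 2, "Both groups complete post-assessment". Both lists contain "Presence of complications" (five items), "Mechanical ventilation status", tolerance of cuff deflation and the CAM-ICU. Section 5 also makes a negative CAM-ICU an entry condition: "Confusion Assessment Method –ICU (CAM-ICU): negative".

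Complications are a named secondary outcome in section 7b. Ventilation status and CAM-ICU are not named there; 7b refers to a codebook for further variables, which is not among the documents. No paired categorical method appears anywhere, and no test is named for comparing the two arms.

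**The concern.** The question 7c poses for a categorical item is whether its frequency differs between Session 1 and Session 2. In paired data only the patients who change status carry information on that: as many should gain the status as lose it if nothing has changed overall. Chi-square and Fisher exact tests assume independent observations and do not use the pairing in this way. The plan respects the pairing for continuous scores and drops it for categorical ones in the same paragraph.

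At stake is the reading of the only test the plan names for any categorical variable, complications included. One layout can report a significant before-after result when every patient was stable. The other can give a p-value that is too large or too small, depending on how the two visits relate.

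**Working it through.** **Inputs from the documents.** 25 patients per arm and 50 in total (7c); both sessions recorded in both arms (4a, E.1 and F.1). The plan states no alpha, event rate or p-value for these tests, so it has no figure of its own to reproduce here. Two-sided alpha of 0.05 and all rates below are assumptions.

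**Notation.** For one binary item, let a = status at both sessions, b = Session 1 only, c = Session 2 only, d = neither. Exact McNemar is a two-sided binomial test of c out of b + c with probability 1/2. Chi-square or Fisher can be applied in two layouts.

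**Layout 1: cross-table of Session 1 by Session 2, [[a, b], [c, d]].** The null is that Session 1 status does not predict Session 2 status.
- Nobody changes: a = 15, b = 0, c = 0, d = 10. Fisher p = 1/C(25,10) = 1/3,268,760 = 3.1e-7. McNemar has no discordant pairs, so p = 1.0.
- Simulation with no true change (20,000 runs; 50% prevalence, 10% switching each way, correlation 0.6): Fisher rejects 86% of the time at n = 25 and 99% at n = 50. Exact McNemar rejects about 1% and 2%.
- The layout also misses real change. With a fall from 80% to 50% and independent visits, n = 25, Fisher rejects 2% and exact McNemar 48%.

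**Layout 2: stacked by time, [[a+b, c+d], [a+c, b+d]].** The null is equal proportions at the two sessions, which is the right question, but each patient is counted as two independent people.
- Positive correlation: a = 5, b = 0, c = 6, d = 14, so 5 of 25 becomes 11 of 25. Fisher on [[5, 20], [11, 14]] gives p = 0.128. McNemar with 6 against 0 gives 2 × (1/2)^6 = 0.031.
- Constant baseline: a = 0, b = 0, c = 6, d = 19, so 0 of 25 becomes 6 of 25. Fisher gives p = 0.022 and uncorrected chi-square 0.009. McNemar is again 0.031.

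**Power of layout 2 against exact McNemar at n = 25 (20,000 runs each, assumed rates).**

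| Session 1 to Session 2 | Stacked Fisher | Stacked chi-square | Exact McNemar |
|---|---|---|---|
| 20% to 40% (21% gain, 1% lose) | 14% | 28% | 36% |
| 4% to 20% | 17% | 40% | 20% |
| 2% to 12% | 3.2% | 18% | 3.4% |
| 0% to 20% | 38% | 76% | 38% |

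The first row is favourable to McNemar: its correlation is (0.19 − 0.20 × 0.40) / √(0.16 × 0.24) = 0.56, against a maximum of 0.61 for those margins. With a low baseline the gain over Fisher is small or nil. The higher chi-square figures with a low baseline go with p-values that are too small, as in the 0-to-6 case.

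**Which n applies to valve use.** In section 4a the standard arm's first valve trial (F.3) is listed after the Session 2 assessment (F.1). Only the early arm can have used the valve between the two assessments, so n = 25 is the relevant size for any before-after effect of the valve.

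**The case against.** The strongest reply is that no stated hypothesis rests on a within-patient categorical change. The one categorical hypothesis about outcomes between sessions or arms, 3b, compares complication rates between arms, where chi-square or Fisher is valid, and 7c may simply be loosely worded for that comparison. The parallel sentence on paired t-tests makes this less likely, and if it is what was meant, the sentence still needs rewriting because it says something else. The point about 3b does stand, and it limits the weight of the finding.

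Three stronger readings are tempting, and the documents do not support them.
- A reader might infer that these tests always have the wrong null. That is true of the cross-table only. The stacked table does test equal proportions; its fault is ignoring the pairing.
- A reader might infer that the plan's p-values are always too large, so that a rise in complications would be missed. With a constant baseline they can be too small, and with rare early complications exact McNemar would detect little or nothing more at n = 25.
- A reader might take power at n = 50 as the power to see harm from the valve. The standard arm has not yet used it at the Session 2 assessment.

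CAM-ICU is also a weak example: it must be negative at entry, so change can go only one way.

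**Conclusion.** The test stated in 7c is wrong as written for paired categorical data. That conclusion does not depend on any assumed rate. The size of the error does: in the cross-table layout it can be extreme (p = 3e-7 with no change at all), and in the stacked layout it is moderate and can run in either direction (0.13 or 0.022 against 0.031 in the two worked cases).

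The consequence is limited. This is a 50-patient pilot, the primary outcome (speech intelligibility) is untouched, and the halting rule in 7d turns on the occurrence of a major complication, not on a p-value. It should be corrected before analysis because the error is clear and the repair is cheap.

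**What to change.** Replace the categorical sentence in 7c with wording such as:

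> Binary variables recorded at Sessions 1 and 2 will be compared within patients, separately by arm, with the exact McNemar test (Stuart-Maxwell test for variables with more than two categories). The numbers of patients gaining and losing the status and the paired difference in proportions with a 95% confidence interval will be reported. Chi-square and Fisher exact tests will be used only to compare independent groups (early versus standard arm), including complications under Hypothesis 3b. For CAM-ICU, the proportion positive at Session 2 will be reported with an exact confidence interval.

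The cost is this change of wording; no extra patients or data are needed. There are two small downsides. Exact McNemar uses only patients who change status, so it is conservative when few do. Each patient's two records must also stay linked, so the research ID assigned at de-identification (section 8d) has to be the same for both sessions.

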## 8. Risks

- a. Medical risks, listing all procedures, their major and minor risks and expected frequency.  
Risks of OWSV use include development of subcutaneous air and air trapping that could lead to respiratory distress.

Administration of questionnaires repeatedly can be burdensome. In addition, questions about their quality of life while mechanically ventilated may be emotionally distressing.

- b. Steps taken to minimize the risks.

Patients will be screened by the tracheostomy nurse practitioner for inclusion in the study, and all patients enrolled in the study will undergo thorough evaluation with an SLP per standard protocol, prior to the trial with the OWSV. Trial of the OWSV will be deferred if the SLP determines that the patient is not an appropriate candidate to trial the OWSV at the time. The SLP will follow standard protocol during OWSV trials of appropriate candidates. OWSV trials will be discontinued and SLP will refer to the medical team if the patient experiences any complications.

During administration of questionnaires, the interviewer will stop the interview and refer to the medical team providing care in the ICU if at any time the participant appears upset or distressed. The interviewer will remain with the participant until she or he has regained emotional equilibrium. If the participant states that he/she is tired and would like to rest, the interviewer will stop the interview and come back at a later time to continue with the interview. The participant may wish to withdraw from the study anytime they choose to.

- c. Plan for reporting unanticipated problems or study deviations.

The PI will discuss any unanticipated problems of study deviations that pertain to the participants' health with the medical team caring for the patient.

Date: 2/06/18

Principal Investigator: [name]

Application Number: **IRB00080981**

- d. Legal risks such as the risks that would be associated with breach of confidentiality.  
Data will be stored in RedCap database that is password protected on the ICTR server. The database can only be accessed by the study team and the PI. Upon, completion of data collection, names and medical record numbers will be removed. A new research ID number will be assigned for analysis. Any document that may re-identify the patient will be destroyed. Once the data are de-identified, then analysis will begin.
- e. Financial risks to the participants.  
N/A

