#### **Specific Aim 3: Determine the effect of early use of the OWSV on clinical outcomes.**

Hypothesis 3a: The increase in the health-related quality of life scores from pre- to post- assessment will be significantly higher in the patients who receive early OWSV compared to those who receive it the traditional way 48 hours after undergoing a tracheostomy.

Hypothesis 3b: There will be no significant changes in the rate of complications between patients receiving early versus standard use of the OWSV.

Hypothesis 3c: Patients who begin to use the OWSV early will have a significantly shorter lengths of stay in the ICU than patients who start using OWSV after 48 hours.

**3. Background** (briefly describe pre-clinical and clinical data, current experience with procedures, drug or device, and any other relevant information to justify the research)

Current standard of care to wait 48 hours following tracheostomy procedure to initiate OWSV assessment and treatment, however, there is scant evidence in the literature justifying this amount of time. 201 patients out 272 patients who received a tracheostomy received SLP consult for in 2014. Based on prior data from the tracheostomy database 30% of mechanically ventilated and / or tracheotomized patients tend to be awake and interactive, and attempt to communicate.

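### The only complications checklist in the plan omits air trapping and respiratory distress and is listed before each valve trial, so if it defines Hypothesis 3b these harms cannot register in the safety comparison

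*Combined protocol and SAP*

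**What the plan says.** The abstract gives the safety of early valve use as the purpose of the pilot. Under Specific Aim 3, Hypothesis 3b is the safety hypothesis: "There will be no significant changes in the rate of complications between patients receiving early versus standard use of the OWSV". Section 7b lists complications as a secondary outcome without defining it and points to a codebook for further variables. The codebook is not part of the documents.

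Section 8a names the risks of the valve: "Risks of OWSV use include development of subcutaneous air and air trapping that could lead to respiratory distress".

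Section 4a (Sequence and timing) has one checklist, headed "Presence of complications". It appears in the Session 1 pre-assessment and the Session 2 post-assessment, for both arms, with the same five items: stomal bleeding, subcutaneous air, stomal infection, pneumothorax and accidental decannulation. Separately, the valve-trial assessment under Session 1 (intervention group) includes "Presence of air trapping" and "Change in vital signs".

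The arms differ in valve exposure. At Session 1, "Control Group receives no further evaluation or treatment during Session 1, which constitutes current standard of care". At Session 2, after the post-assessment, "Control Group completes initial SLP evaluation and OWSV trial", while the intervention group has its second trial. Session 3 lists no complications checklist.

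**The concern.** A safety comparison should count the harms that the protocol itself expects from the device. Here the stated valve risks and the stated complications list share only subcutaneous air. If Hypothesis 3b is analysed from the list, a patient with air trapping or respiratory distress during a valve trial adds nothing to the complication rate unless a listed event also occurs. The hypothesis predicts no difference, so leaving these events out could help it to appear confirmed.

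The two harms are not in the same position. Air trapping is written down somewhere, so an analysis rule could bring it in later. Respiratory distress has no item of its own, and a study form that never asked for it cannot supply it afterwards.

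**Working it through.** **1. Named risks against the list and the trial assessment (sections 8a and 4a)**

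| Risk named in 8a | On the five-item checklist? | Recorded in the valve trial? |
|---|---|---|
| Subcutaneous air | Yes | Not as a trial item |
| Air trapping | No | Yes |
| Respiratory distress (as a consequence of air trapping) | No | No item; vital signs are an indirect signal, with no threshold given |

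No section says that a valve-trial finding counts as a complication.

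**2. Listed order of checklist and valve trial (section 4a)**

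- Session 1: checklist in both arms, then the early arm's first valve trial.
- Session 2: checklist in both arms, then the early arm's second trial and the control arm's first.
- Session 3: further valve trials as appropriate, with no checklist listed.

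The Session 2 checklist can therefore pick up listed events that follow the early arm's first trial. No listed checklist follows the control arm's first trial. For the five listed items, the Session 2 comparison is between patients offered a valve trial and patients not yet offered one.

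**3. Removal (sections 4f and 7d)**

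Patients leave the study if a change in condition prevents the valve trial from continuing or prevents cuff deflation. An early-arm patient in distress could leave before the Session 2 checklist.

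**4. Sample size**

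Section 7c: about 55 eligible patients less 10% who decline gives 55 × 0.90 = 49.5, rounded to 50, or 25 per arm. This reproduces the plan's figure. It is a feasibility figure. No power, alpha or margin is stated.

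**5. Chance that events occur and go uncounted**

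The documents give no event rates, so these are assumptions. With true early-arm rate p, P(at least one event in 25) = 1 − (1 − p)^25:

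- p = 5%: 1 − 0.95^25 = 72%
- p = 10%: 1 − 0.90^25 = 93%
- p = 20%: 1 − 0.80^25 = 99.6%

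**6. What the test could show if the events were counted**

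Assume a two-sided Fisher exact test at 0.05, 25 per arm, a 5% rate of listed events in both arms, and added harms independently in the early arm only at rate a. The early-arm rate is 1 − 0.95 × (1 − a). Exact power, by enumeration:

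| a | Early-arm rate | Power, 5% listed rate | Power, 10% listed rate |
|---|---|---|---|
| 5% | 9.8% | 1% | 3% |
| 10% | 14.5% | 6% | 7% |
| 20% | 24.0% | 33% | 25% |
| 30% | 33.5% | 66% | 50% |

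(The early-arm rates shown are for the 5% listed rate.)

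For single results, 5/25 against 0/25 gives p = 0.0502 and 6/25 against 0/25 gives p = 0.022. Zero events in 25 is compatible with a true rate up to 1 − 0.05^(1/25) = 11.3% (one-sided 95% limit), or 1 − 0.025^(1/25) = 13.7% (upper limit of the two-sided 95% interval).

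**The case against.** The strongest reply is that no section says the five-item list is the Hypothesis 3b endpoint. The codebook may define complications more widely. The protocol itself uses the word more broadly: section 8b has valve trials discontinued when complications arise, and section 7d halts the study for major complications of an early trial. Both treat valve-trial events as complications. This stands. The link from list to hypothesis is an inference from the only list present, so the consequence is conditional. A reader might infer that a site would certainly score a trial stopped for air trapping as free of complications, and the documents do not establish that.

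Second, much of the information is collected. Air trapping, vital signs and duration of tolerance are valve-trial items, and subcutaneous air is on the checklist. This also stands. For air trapping the gap is a missing counting rule. For distress it is a missing item.

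Third, a reader might infer that the comparison is biased towards no difference throughout, with the other four items merely diluting a valve effect. The documents do not support that. The abstract ties the safety of early use to the type of tracheostomy procedure and its postoperative complications, so a general tracheostomy list fits the stated rationale. For listed events the order works the other way, because the control arm's first trial comes after its last checklist.

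Fourth, complications are a secondary outcome in a 50-patient pilot, and added items would seldom change a significance test. That is correct, and it argues for reporting rates with intervals. It does not justify leaving named harms out of those rates.

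**Conclusion.** The mismatch is plain on the text. Section 8a names air trapping that could lead to respiratory distress; the only complications list contains neither, and no listed checklist follows the control arm's first valve trial. If the list defines Hypothesis 3b, air-trapping and distress events contribute exactly zero to the comparison, whatever their number. Under the assumed rates of 5% to 20%, at least one such event in the early arm would be likely (72% to 99.6%).

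The conclusion rests on three things: the checklist being the endpoint, the listed order being the order of conduct, and assumed event rates. It does not extend to saying that air trapping goes unrecorded, that no valve risk is counted, or that the net bias has a known direction. Adding the items lets the harms be seen; it does not make 25 per arm enough to demonstrate safety by a non-significant test.

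**What to change.** - Define the complications outcome for Hypothesis 3b in the protocol. Add air trapping and respiratory distress, each with a written definition, and include a valve trial stopped for either. If the codebook already does this, say so in the protocol.
- Keep the existing checklist as a pre-trial baseline and complete it again after each valve trial in both arms.
- Keep patients who are removed from the study in the safety count.
- Report valve-related events (subcutaneous air, air trapping, distress) separately from the other tracheostomy complications. Compare first valve trial with first valve trial, Session 1 in the early arm against Session 2 in the control arm. Pooling all trials would give the early arm an extra chance to score.
- State the denominators. Section 8b allows a trial to be deferred, so show both the number randomised and the number who had a trial.
- Report each arm's rate and the difference with confidence intervals, as a comparison between arms. Section 7c describes the categorical tests only as pre against post. Do not infer safety from non-significance.

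The cost is protocol and form wording, one new item (distress, or a trial stopped), and a repeat checklist after each trial. Air trapping and vital signs are already trial items in section 4a, though that list is written out only for the intervention group at Session 1 and should be stated for every trial. The complication rate may look less favourable.
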